11.1.1 Other Analysis of Primary Efficacy Variable

The ANCOVA Analyses of the primary efficacy variable will also be performed using the PP population and with no imputations for missing Week 4 Follow-Up weekly mean of the average daily bladder pain NRS.

Average daily 24-hour pain NRS and the corresponding change from baseline values will also be summarized for each week post randomization for the Treatment 1 Period (see Table 17.2.1–1). For each weekly (mean) change from baseline values, the ANCOVA analysis outlined for the primary timepoint will be applied without any imputation for missing values.

A sensitivity analysis using a mixed-effects model for repeated measures (MMRM) (Mallinckrodt et al, 2001a and 2001b) based on all post-baseline weekly mean data up to Treatment 1 Week 4 Follow-Up, will be performed to compare treatment effect at each post-baseline week (see Table 17.2.1–1). The MMRM analysis will include treatment group, assessment week, and treatment group–by-assessment week interaction as factors and baseline value as covariate. An unstructured covariance matrix will be used to model the correlation over time in change from baseline values for the primary efficacy variable.

Plots of weekly mean of the average daily bladder pain values and the associated change from baseline values will be presented by treatment group over time.

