with 7 patients diagnosed with IC with HL and the remaining the 9 patients with IC/BPS. Cohort 1 (200 mg) enrolled 9 patients, and 8 patients completed. Cohort 2 (650 mg) enrolled 9 patients and all 9 patients completed. All enrolled patients had LiRIS inserted and indwelling in the bladder for up to a 14-day period and were followed for safety assessments for 14 days after removal of LiRIS. Cohort 2 (650 mg) patients also had additional long-term safety and efficacy assessments at 60 and 90 days postinsertion. The results of this study show that LiRIS 200 mg and LiRIS 650 mg are well tolerated with the most common adverse events (> 20 % overall) being dysuria, haematuria, and bladder pain. The majority of adverse events observed were mild or moderate in intensity. One serious adverse event of "suicidal ideations" was reported and deemed to be unrelated to LiRIS or the cystoscopy procedure. LiRIS 650 mg resulted in higher plasma concentrations and greater amount of lidocaine and 2,6-xylidine recovered in urine compared with LiRIS 200 mg. However, these plasma concentrations of lidocaine after LiRIS insertion were much lower than those associated with toxicity (> 5.0 μ g/mL). 2,6-xylidine concentrations were on average < 10% of the observed plasma concentrations of lidocaine. Overall, both LiRIS 200 mg and LiRIS 650 mg appear to be safe, tolerable, and efficacious in the treatment of bladder pain and irritative voiding symptoms. A subanalysis of the IC with HL patients, showed improvement in inflammatory findings with 6 out of the 7 patients enrolled with pre-existing HLs, revealing a resolution of lesions at the time of LiRIS removal. This interesting finding might be attributed to the antiinflammatory properties of lidocaine described earlier.

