5.3 Methods for Masking/Blinding

All study treatments (active and placebo) and packaging will be identical in order to maintain masking of the study. The study treatment will be identified as an investigational compound. The study number and kit number will be identified on the unit label.

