5.6 Treatment Regimen and Dosing

5.6.1 Treatment 1

Eligible patients will be randomized on Randomization/Day 0 to receive Treatment 1, LiRIS 400 mg/LiRIS 400 mg; LiRIS Placebo/LiRIS Placebo or LiRIS Placebo/LiRIS 400 mg (Section 5.4). Patients will have the Treatment 1, 1st IP inserted on Randomization/Day 0 and removed on Day 14. On the same day, following the 1st IP removal, the 2nd IP (LiRIS 400 mg or LiRIS Placebo) will be inserted and subsequently removed on Day 28. Patients will be followed for 20 weeks post IP removal for additional safety and efficacy assessments. In the event that a patient does not receive Treatment 2, they will exit the study at Treatment 1 Week 20 Follow-up Visit.

5.6.2 Treatment 2

All patients will receive LiRIS 400 mg for their second treatment. Patients may request, qualify, and receive Treatment 2 IP from Week 4 Follow-up until Week 20 of Treatment 1. In the event that the Treatment 2 IP cannot be inserted on the day of qualification, Treatment 2 may be rescheduled within 14 days of qualification. The LiRIS will be inserted on Treatment 2/Day 0, and will be removed on Day 14. Patients will be followed for 4 weeks post-removal and will be exited from the study.

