Study 201025-001 is a phase 2 multicenter, randomized, double-blind, placebocontrolled, study to evaluate the safety and efficacy of the LiRIS 400 mg in female patients with interstitial cystitis (IC) with Hunner's lesions (HL). This study includes up to 2 treatments. To receive Treatment 1, patients will be randomized in a 2:1:1 ratio to 1 of 3 treatment groups receiving over a 28-day treatment period either:

Group 1: 2 consecutive LiRIS 400 mg (N = 38)

Group 2: 2 consecutive LiRIS Placebo (N = 19)

Group 3: LiRIS Placebo followed by LiRIS 400 mg (N = 19)

Patients who qualify for Treatment 2, will receive LiRIS 400 mg over a 14-day treatment period followed by 4 weeks of observation until exit. Patients will be stratified based on screening baseline pain score (≤ 5 or > 5).

The primary analysis will be conducted at the time when the last patient completes the primary timepoint that is Week 4 following removal of the Treatment 1 second investigational product (IP) removal. The final analysis will be conducted when all patients complete or exit the study. For each analysis timepoint all data available will be included in the analysis. The analyses outputs to be included will be the same for the primary and final analysis timepoints. The schedule of evaluations for Study 201025-001 is presented in Table 4–1. The double-blind treatment period starts with the first IP insertion and ends with the last assessment prior to Treatment 2 IP insertion or Exit visit in the Treatment 1 period.

Table 4–1.

Schedule of Evaluation for Study 201025-001

Table 4–1.

Schedule of Evaluation for Study 201025-001

27MAR2018 CSR 201025-001

Table 4–1.

Schedule of Evaluation for Study 201025-001

5.0 **OBJECTIVES**

The study objective is to evaluate the safety and efficacy of a 28-day period of continuous release of lidocaine inserted into the bladder utilizing 2 consecutive LiRIS 400 mg compared with placebo for the treatment and corresponding symptoms of IC with HL in female patients. The clinical hypotheses is that a 28-day period of continuous release of lidocaine inserted into the bladder utilizing two consecutive LiRIS 400 mg will have an acceptable safety profile and will be more efficacious than placebo for the treatment and corresponding symptoms of IC with HL in female patients.

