11.2 SECONDARY EFFICACY PARAMETER(S)

A standardized video capture protocol for bladder mapping will be followed in order to assess any changes in the number, the size and the severity, of lesions during the study as a result of treatment. The video image will be captured at baseline and at scheduled post-baseline visits. These will be used to categorize the change from baseline bladder images to categories such as complete responders, partial responders, stable disease and worsened disease. The number and percentage of patients in each category will be analyzed by treatment group. Furthermore, for each category of responders, at each post-baseline visit, the number of patients with 1, 2 and \geq 3 point reduction in daily average pain NRS will be summarized by treatment group.

During each cystoscopy, the investigator will count the number of lesions visible while preforming the bladder scan for bladder mapping. The number of lesions and the change from baseline in the number of lesions will be summarized for each relevant visit by treatment group.

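### Before the Day 14 device exchange the two placebo-first groups receive the same blinded treatment, but the SAP does not pre-specify pooling them, so the early-week LiRIS v placebo contrast uses 18 controls where 36 are available

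*SAP*

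**What the plan says.** SAP 4.0 states that "patients will be randomized in a 2:1:1 ratio to 1 of 3 treatment groups": two LiRIS, two placebo, or placebo followed by LiRIS, with 38, 19 and 19 patients. Protocol 5.6.1 fixes the timing: "Patients will have the Treatment 1, 1st IP inserted on Randomization/Day 0 and removed on Day 14", with the second device inserted the same day. On masking, Protocol 5.3 says "All study treatments (active and placebo) and packaging will be identical in order to maintain masking of the study".

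SAP 11.1 sets the primary hypotheses for two LiRIS against two placebo. It specifies an ANCOVA with treatment and the pain stratum as factors and baseline pain as covariate. SAP 11.1.1 then extends this model to every week after randomisation in Treatment 1: "the ANCOVA analysis outlined for the primary timepoint will be applied without any imputation for missing values". The same section adds an MMRM with treatment, week and their interaction, to compare treatments at each post-baseline week.

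For lesions, SAP 11.2 says: "The number of lesions and the change from baseline in the number of lesions will be summarized for each relevant visit by treatment group". Protocol 6.5.8 has the investigator count lesions at each cystoscopy, and SAP 12.5.3 places cystoscopies on insertion and removal days.

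**The concern.** From Day 0 to the exchange, Groups 2 and 3 differ only in a future assignment that nobody at the site knows. They are one randomised, blinded placebo condition. A contrast that uses only Group 2 as control in that period is valid and unbiased, but it leaves half of the concurrent placebo patients out of the comparison.

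The early period is of interest in its own right. Protocol 1.4 motivates the lesion programme with an uncontrolled finding in an open-label study of single devices (200 mg or 650 mg): 6 of 7 patients with Hunner's lesions were described as "revealing a resolution of lesions at the time of LiRIS removal", after up to 14 days in place. Group 1 against all placebo-first patients, at removal of the first device, is the closest controlled counterpart that this trial offers. The protocol summary says that the primary analysis is meant to support further development, so the precision of the early weekly estimates is worth having when it costs nothing.

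**Working it through.** **Inputs.** Evaluable patients 36 / 18 / 18, difference 1.152, SD 1.67, 1-sided 0.05, stated power 76% (Protocol 7.7; SAP 14.0 and 15.0). Protocol 7.7 says that the SD is that of the raw Week 4 Follow-up pain score in an open-label study. Neither document gives an SD or an expected difference for Weeks 1-2.

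**Which weeks fall before the exchange.** The weekly window table is not in the public text, but the windows can be inferred. SAP 17.1 counts the first insertion as Day 1, so the protocol's Day 14 exchange is SAP Day 15. SAP 11.1 places Week 4 Follow-up at Days 50-56. Since 50 = 7×7 + 1 and 56 = 7×8, this is the eighth 7-day block from Day 1. On that pattern Week 1 is Days 1-7 and Week 2 is Days 8-14, and both end before an on-schedule exchange.

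**Step 1: reproduce the plan's figure.**
- SE = 1.67 × √(1/36 + 1/18) = 0.482
- Noncentrality = 1.152 / 0.482 = 2.39, with 52 df
- Power, noncentral t, 1-sided 0.05 = 76.2%. The stated 76% reproduces.

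**Step 2: pool the placebo-first groups (18 + 18 = 36).**
- SE = 1.67 × √(1/36 + 1/36) = 0.394
- Noncentrality = 1.152 / 0.394 = 2.93, with 70 df
- Power = 89.5%
- Ratio of SEs = 0.394 / 0.482 = 0.816, about 18% smaller
- Information ratio = (1/36 + 1/18) / (1/36 + 1/36) = 1.5
- Half-width of the 90% CI falls from 0.81 to 0.66
- Difference detectable with the same 76.2% power falls from 1.152 to 0.94

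The 0.816 and 1.5 depend only on the sample sizes and a common SD. The power figures also need the Week 4 difference and SD to apply at Weeks 1-2.

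**Step 3: vary the SD, difference held at 1.152.**

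| SD | 36 v 18 | 36 v 36 |
|---|---|---|
| 1.3 | 91.7% | 98.1% |
| 1.67 | 76.2% | 89.5% |
| 2.0 | 62.7% | 78.1% |
| 2.5 | 47.2% | 61.5% |

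**Step 4: does keeping Group 3 in the model already recover this?** No. If Group 3 contributes only to the residual variance, the SE stays at 0.482 and the error df rises to about 69. Power is then 76.5%, against 76.2%.

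**Step 5: can the planned models deliver the pooled comparison?** Yes. A contrast with weights 1, −1/2, −1/2 on Groups 1, 2 and 3 gives the placebo side a variance factor of (1/4)(1/18 + 1/18) = 1/36, the same as pooling when the two groups are equal in size.

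**The case against.** The strongest reply is that nothing is lost that matters. These are supportive weekly analyses in a phase 2 trial with no multiplicity adjustment (Protocol 7.3). Efficacy is to be analysed as randomised, and keeping three groups throughout is unbiased. Group 3 is not discarded, as a reader might infer: treatment is a factor in one ANCOVA and one MMRM, so Group 3 presumably stays in both models and has its own weekly mean. It is left out of one contrast, not out of the analysis. All of that stands and limits the weight of the point. It does not restore the lost precision (Step 4), and pooling patients who were randomised to the same first device is also an as-randomised comparison.

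A second reply is that pooling may be planned somewhere unseen. The amendment log mentions arm comparisons in Protocol 7.3.2.3 and 7.3.2.4, which are not in the public text. SAP 11.1 also has a second adjusted difference whose arm names are garbled. In addition, SAP 11.1.1 reaches the Placebo/Placebo comparator only by reference to SAP 11.1. So the claim must be that no visible passage pools the groups, not that the plan certainly omits it.

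A third reply concerns lesions. SAP 11.2 plans summaries by group at relevant visits, with no between-group test at Day 14. Protocol 7.3.2.2 places the possible ANCOVA of secondary variables at Week 4 Follow-up. A power gain for a Day 14 lesion test would therefore describe an analysis that the visible plan does not contain, with response rates that the documents do not supply. That objection succeeds, and the lesion part reduces to a clearer descriptive display.

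**Conclusion.** The point holds as an inexpensive improvement to supportive analyses. For weekly pain before the second insertion, the visible SAP sets LiRIS against 18 evaluable placebo patients when 36 concurrent, identically treated and blinded controls are available. Given a common SD, the SE is about 22% larger than it need be (0.482 / 0.394 = 1.22). The gain in power from 76.2% to 89.5% assumes that the Week 4 difference and SD carry over. Across SDs of 1.3 to 2.5 the gain is between 6.4 points (91.7% to 98.1%) and 15.4 points (62.7% to 78.1%) at the four values tabulated.

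Two stronger readings are not supported. First, a reader might infer that the early weeks are the only test of one LiRIS against placebo. They are not: after the second device, Group 3 v Group 2 is also a randomised, blinded comparison of one LiRIS with none, although at 18 v 18 it has 64.9% power on the same inputs. Second, a reader might link the point to the protocol's aim of exploring two LiRIS against one. Weeks 1-2 cannot address that, pooled or not, because no patient has yet had a second device. The primary Week 4 comparison is unaffected, since Groups 2 and 3 differ by then.

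**What to change.** - **SAP 11.1.1:** for weekly pain assessments before the second insertion, pre-specify a contrast of Group 1 with Groups 2 and 3 combined, labelled LiRIS Placebo, from the same ANCOVA and MMRM, with its 90% CI. Define eligibility by each patient's actual date of second insertion, so that an early exchange does not bring post-exchange days into the pooled weeks.
- **SAP 11.2:** add a pooled-placebo column to any summary of lesion counts or response categories taken at the Day 14 removal, before the second insertion.
- **Unchanged:** the three-group displays at all timepoints and the primary Week 4 analysis.

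The cost is a sentence or two in the SAP and a few table columns, with no new data, patients or procedures. It should be written before unblinding. Pooling chosen after the separate Group 2 and Group 3 results are known would look selective.

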11.2 SECONDARY EFFICACY PARAMETER(S)

A standardized video capture protocol for bladder mapping will be followed in order to assess any changes in the number, the size and the severity, of lesions during the study as a result of treatment. The video image will be captured at baseline and at scheduled post-baseline visits. These will be used to categorize the change from baseline bladder images to categories such as complete responders, partial responders, stable disease and worsened disease. The number and percentage of patients in each category will be analyzed by treatment group. Furthermore, for each category of responders, at each post-baseline visit, the number of patients with 1, 2 and \geq 3 point reduction in daily average pain NRS will be summarized by treatment group.

During each cystoscopy, the investigator will count the number of lesions visible while preforming the bladder scan for bladder mapping. The number of lesions and the change from baseline in the number of lesions will be summarized for each relevant visit by treatment group.

12.0 SAFETY ANALYSES

The safety analysis will be performed using the Safety Population. The safety parameters will include adverse events (AEs) and clinical laboratory and vital signs parameters, physical and pelvic assessments. For each clinical laboratory and vital sign parameters, the last non-missing safety assessment before the first Treatment 1 IP insertion will be used as the baseline for all analyses of that safety parameter. Continuous variables will be summarized by number of patients and mean, SD, median, minimum, and maximum values. Categorical variables will be summarized by number of patients.

All safety analyses will be performed using the safety population. For such analyses, subjects will be analyzed according to actual treatment received at the study treatment visit (i.e., "as treated" rather than "as randomized").

The following safety analyses will be performed unless otherwise mentioned:

- Summaries by treatment group and overall for the Treatment 1 period
- Summaries for patients who participated in both the Treatment 1 period and Treatment 2 period by treatment group and overall patient population. In this analysis, the treatment groups will be the safety treatment groups.

12.1 **ADVERSE EVENTS**

Adverse events will be coded by system organ class and preferred term using the *Medical Dictionary for Regulatory Activities*, version 18.1 or newer.

An AE will be considered a treatment-emergent adverse event (TEAE) if it was present after the first dose of study treatment or was present before the date of the first dose of study treatment and increased in severity after the first dose of study treatment or became serious after the first dose of study treatment. If more than 1 AE was reported before the first dose of study treatment and coded to the same preferred term, the AE with the greatest severity will be used for comparison with the AEs occurring during the study period.

Analysis of the incidence of TEAEs will be performed for the Treatment 1 Period using the Safety population. For the cohort of safety patients that received Treatment 2 IP, the incidence of TEAEs will be summarized over the Treatment 2 Period and over the entire study period (Treatment 1 and 2 period). The following rules will be used to count TEAEs at each treatment period.

- For the analyses of TEAEs by treatment period, an event will be counted once in the particular period if the onset of this event begins during that corresponding period.
- If an event occurs during the Treatment 1 period and continues to the Treatment 2 period without increasing in severity, this event will be counted as an event during the Treatment 1 period but will not be counted again as an event in the Treatment 2 period.
- If an event occurs during the Treatment 1 period or earlier and continues to the Treatment 2 period and the severity increases to a grade that is greater than the maximum severity of the Treatment 1 period or the pre-treatment period or becomes serious in Treatment 2 period then the event will be counted as an event in the Treatment 2 period.

For each treatment phase and for the overall treatment period the number and percentage of patients reporting TEAEs in each treatment group will be tabulated by descending percentage in any group, by system organ class and preferred term, and further categorized by severity and causal relationship to the study treatment. If more than 1 AE is coded to the same preferred term for the same patient, the patient will be counted only once for that preferred term using the greatest severity and strictest causality for the summarization by severity and causal relationship. All AE summary tables will be by treatment group and the overall safety population.

The total number of TEAEs by severity and causal relationship to the study treatment will be summarized by treatment group.

The number and percentage of patients who have Treatment emergent SAEs will be summarized by preferred term and treatment group. In addition, the incidence of treatment emergent SAEs that led to death will be summarized separately by preferred term for each treatment group.

The number and percentage of patients in the Safety Population who have AEs leading to premature discontinuation of the study treatment will be summarized by preferred term and treatment.

Pretreatment AEs are the AEs that occur after signing of the informed consent (IC) and prior to first dose of study medication. Such AEs will be presented in a patent listing.

The table below presents the preferred terms identified to be of special interest for lidocaine treatment. Since lidocaine has a short half-life, for these AEs to be considered of special interest for lidocaine treatment and to be further summarized in a table they need to occur on or after the day of IP insertion and up to the day after the IP removal. For Treatment 1 period it will be up to the day after the 2nd IP removal while for Treatment 2 it will be the day after the IP removal. The summary table will present such events by treatment group and overall. This table will be updated prior to database lock for consistency with the MedDRA version (version presented below is 18.1) that will be used for the analysis.

MedDRA v18.1 PT for AEs associated with of lidocaine toxicity

MedDRA Preferred term Dizziness

- Somnolence Nervousness Feeling cold Feeling hot Confusional state Cardiac arrest Circulatory collapse Seizure Vision blurred Diplopia Hypoaesthesia Paraesthesia oral
- Hypoaesthesia oral Hypotension Bradycardia Respiratory arrest Respiratory depression Tinnitus Tremor Muscle twitching Loss of consciousness Vomiting

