9.1 Definitions

9.1.1 Adverse Event

An adverse event is any untoward medical occurrence in a patient or clinical investigation subject administered a pharmaceutical product and that does not necessarily have a causal relationship with this treatment. An adverse event can therefore be any unfavorable and unintended sign (including an abnormal laboratory finding), symptom, or disease temporally associated with the use of a medicinal (investigational) product, whether or not related to the medicinal (investigational) product. In addition, during the Screening period, adverse events will be assessed regardless of the administration of a pharmaceutical product.

Note: Adverse events must be collected once informed consent has been obtained, regardless of whether or not the patient has been administered study IP.

Progression of treatment indication including new or worsening of anticipated clinical signs or symptoms, which are collected as clinical efficacy variables and assessed as unequivocally associated with the disease progression and/or lack of efficacy, should NOT be reported as

adverse events unless the disease progression is greater than anticipated in the natural course of the disease.

Adverse events will be assessed, documented, and recorded in the eCRF throughout the study (ie, after informed consent has been obtained). At each visit, the investigator will begin by querying for adverse events by asking each patient a general, non-directed question such as "How have you been feeling since the last visit?" Directed questioning and examination will then be done as appropriate. All reported adverse events will be documented on the appropriate eCRF.

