The data derivations and definitions listed in this section are to be applied to all analyses described in this analysis plan, unless otherwise stated.

- In this study there are two treatment periods:
 - Treatment period 1: for patients that just receive treatment in the randomized and blinded phase of the trial, it covers the period from the first Treatment 1 IP insertion to study exit. In contrast, for patients that receive IP insertions in both the randomized phase of the study (Treatment 1) and the open label phase of the study (Treatment 2) it covers the period from first Treatment 1 IP insertion up to Treatment 2 IP insertion,
 - Treatment period 2: covers the period from Treatment 2 IP insertion to study exit.
- Study days for each treatment period X (X=1 or 2) will be calculated as:
 - Study day of Treatment X = visit date (day 1 of Treatment X) + 1.
- The baseline value of an assessment will be the last value recorded prior to the patient being inserted with first Treatment 1 IP on Day 1.
- Unless otherwise stated no imputation will be performed for missing data. All analyses will be based on the observed data.
- For analyses that are by stratification factor, actual stratification levels rather than randomization stratification levels will be used.
- Data will be pooled across the investigational sites.
- Descriptive statistics for continuous/ordinal data include the sample size (N), mean, standard deviation (SD), median, minimum (Min), and maximum (Max) and 95% confidence intervals.
- Summary statistics for categorical variables include sample size (N), frequency count (n), and percentage (%).

17.2.1 **Pain Data Derivations**

A pain assessment tool will be utilized in the study to capture the average daily pain and the daily worst pain scores on an electronic hand held device. Patients will be asked to rate their daily pain on a pain NRS consisting of an 11 point integer scale ranging from 0 for "no pain" to 10 for "worst pain imaginable". The pain assessment will continue every day up to and including the day prior to the Exit visit.

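### SAP 12.1's TEAE definition takes in unchanged screening events, and its counting rules give screening events that worsen in Treatment 1 no place in the Treatment 1 table

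*SAP*

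**What the plan says.** Protocol 9.1.1 starts AE collection at consent: "Adverse events must be collected once informed consent has been obtained, regardless of whether or not the patient has been administered study IP". Screening lasts up to 4 weeks (Protocol 3, SAP 5.0), so the database will hold events with onset before any IP.

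SAP 12.1 then does three things.

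- It defines a TEAE. The first limb is "An AE will be considered a treatment-emergent adverse event (TEAE) if it was present after the first dose of study treatment". The alternative limb covers an event that "was present before the date of the first dose of study treatment and increased in severity after the first dose of study treatment", or that became serious after that dose.
- It sets a baseline for comparison. Where several pre-dose events share a preferred term, "the AE with the greatest severity will be used for comparison with the AEs occurring during the study period".
- It gives counting rules, introduced by "The following rules will be used to count TEAEs at each treatment period". Under the first rule, "an event will be counted once in the particular period if the onset of this event begins during that corresponding period". The second keeps an event that carries over from Treatment 1 without worsening out of the Treatment 2 count. The third handles worsening or becoming serious, and begins "If an event occurs during the Treatment 1 period or earlier and continues to the Treatment 2 period and the severity increases"; such an event is counted in Treatment 2.

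SAP 17.2 fixes the start of Treatment 1. For a patient who receives only Treatment 1, "it covers the period from the first Treatment 1 IP insertion to study exit"; for a patient who goes on to Treatment 2, the start is the same and the end is the Treatment 2 insertion. SAP 12.1 sends pretreatment AEs to a listing.

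**The concern.** The definition and the counting rules do not classify the same events in the same way.

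The first limb tests presence after dosing, not first appearance after dosing. Mild dysuria that begins in screening and runs on unchanged past insertion meets it. The worsening limb is then redundant, because any pre-dose event that worsens after dosing is also present after dosing. The comparison with the worst pre-dose severity also loses its purpose.

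The counting rules have a different gap. Haematuria that is mild in screening and becomes severe with the IP in place is a TEAE by the definition. Its onset lies before Treatment 1, and the only worsening rule concerns Treatment 2. Had the same event worsened in Treatment 2, it would be counted.

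Treatment 1 is the only randomised safety comparison, since every patient who enters Treatment 2 receives LiRIS 400 mg (Protocol 5.6.2). The plan therefore provides for worsening in the uncontrolled period and has no counting rule for it in the controlled one. The patients enter with lower urinary tract symptoms (Protocol 4.3), and bladder pain, dysuria, haematuria and UTI were the events seen in 10% or more of patients in the earlier LiRIS 400 mg trial (Protocol 1.4). Worsening of an existing urinary event is thus a plausible form of device or procedure harm.

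**Working it through.** The plan states no AE count to reproduce, so the check is logical. Five event histories are passed through the rules. The inputs are the two limbs of the definition and the counting rules (SAP 12.1) and the start of Treatment 1 at first insertion (SAP 17.2). A worsening is treated as one continuing record that keeps its onset date, which is how SAP 12.1 describes it.

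| Event history | TEAE, definition as written | TEAE, first limb read as new onset | Assigned to Treatment 1 by the counting rules | Treatment 1 count after the fix |
|---|---|---|---|---|
| Screening onset, resolved before insertion | no | no | no | no |
| Screening onset, continues unchanged | **yes** | no | no | no |
| Screening onset, worsens in Treatment 1 | yes | yes | **no** | yes |
| Screening onset, becomes serious in Treatment 1 | yes | yes | **no** | yes |
| Onset in Treatment 1 | yes | yes | yes | yes |

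Reading across:

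1. *Definition alone.* The two candidate meanings of the first limb differ only in the second row, the unchanged screening event. The written text includes it. A summary built on the definition without the onset rule would overcount those events and miss none.
2. *Definition plus onset rule.* Only the last row is assigned to Treatment 1, whichever way the first limb is read. The third and fourth rows are lost, although both readings of the definition call them TEAEs. The second row also drops out, so nothing is overcounted.
3. *Both errors together.* No single reading gives both in the Treatment 1 table. The rule that removes worsened events also removes unchanged ones.
4. *Where the overcount could appear.* It needs a summary made without the onset rule. The sentence in SAP 12.1 on the total number of TEAEs by severity and causality names no period, so it is a candidate.

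On scale, the planned arms are 38, 19 and 19 (SAP 4.0). One patient moves an incidence by 1/38 = 2.6 percentage points or 1/19 = 5.3 percentage points. These are step sizes per misclassified patient. They do not estimate how many patients would be misclassified.

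**The case against.** The best defence is that the passage, read as a whole, means new onset or worsening. The literal reading makes one limb redundant and the severity comparison pointless, which is evidence against it as the intended meaning. The first counting rule says *if*, not *only if*, and the rules may exist mainly to prevent double counting between periods. A site might enter a worsening as a new AE with its own onset date, and the onset rule would then count it. Protocol 7.3.3 lists all AEs for individual patients, so no event vanishes from the report. Protocol 9.1.1 also excludes worsening of anticipated symptoms that are collected as efficacy variables and judged unequivocally due to progression or lack of efficacy, unless progression exceeds what is anticipated. An affected event must in addition start within the short screening window, persist to insertion and then worsen.

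Some of this stands. The intent behind the definition is fairly clear, the Protocol 9.1.1 exclusion removes part of the pathway, and the number of affected events may be small. The rest is weaker. If onset were not decisive, the separate Treatment 2 worsening rule would have no work to do. The documents do not say that worsening is recorded as a new event, and SAP 12.1 speaks of one event that continues and increases in severity. A patient listing does not correct an incidence table.

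Three stronger inferences are tempting but unsupported. A reader might conclude that the Treatment 1 table is wrong in both directions; as shown, the two errors are alternatives there. A reader might conclude that the treatment-emergent SAE tables are padded with pre-existing events; SAP 12.0 makes by-period summaries the default, and nothing shows that the SAE tables depart from it. A reader might take 5.3 or 2.6 points as the bias, or set them against the 10% figure from the earlier trial; that figure describes common events there and is not a threshold in this SAP.

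**Conclusion.** The inconsistency is real and lies in the controlling text. The definition is over-inclusive as written. The counting rules assign no period to a screening event that worsens or becomes serious in Treatment 1, although a matching provision exists for Treatment 2. The likely consequence is an undercount of such events in the Treatment 1 table; any overcount is confined to summaries made without the onset rule.

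The undercount rests on two assumptions: that the onset rule is applied as the criterion for assigning events to a period, and that a worsening keeps the original onset date. If either fails, it shrinks or disappears. The size cannot be computed from the documents. The point should be settled because the definition and the counting rules give opposite answers for the same event, and the choice would otherwise be made in programming.

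**What to change.** Make three changes in SAP 12.1.

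- **Definition:** a TEAE is an AE not present before the first IP insertion, or present before it and increased in severity or became serious on or after it.
- **Counting rule:** add a Treatment 1 rule parallel to the Treatment 2 rule: a pre-treatment event that increases above its maximum pre-treatment severity or becomes serious during Treatment 1 is counted in Treatment 1.
- **Scope:** apply this one definition to all TEAE and treatment-emergent SAE tables, and name the period covered by the total-TEAE count.

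It would help to state whether a worsening is kept on the existing AE record or entered as a new one, since the count depends on it.

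The cost is a few sentences and a programming flag, with no new data. The change should be in place before the primary analysis, because SAP 4.0 uses the same outputs for the primary and final analyses.
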